1.2.3 Compare caregiver quality of life

2.0 BACKGROUND, RATIONALE

Hematopoietic stem cell transplantation (HCT) is a complex medical treatment that causes significant symptom burden for patients and their caregivers. Patients receive chemotherapy and/or radiation therapy prior to transplant to eradicate the underlying disease and provide immunosuppression. While the myelosuppressive or myeloablative conditioning regimens used prior to transplant provide medical support to treat underlying disease and provide immunosuppression, they can cause the development of physical,¹ psychological,² and nutritional challenges³⁻⁵ that can impact a patient’s short- and long-term wellness. Allogeneic HCT is associated with treatment related mortality (TRM) ranging from 20-30%.⁶ TRM is particularly high in patients with advanced age, decreased functional status, and/or comorbid conditions such as depression or organ dysfunction. While evaluation of organ dysfunction is required part of pre-transplant workup (echocardiogram, pulmonary function testing, etc.), decreased physical function, cognitive deficits, depression, poor nutrition, and lack of

A Research Program Targeting Pre-, Peri-, and Post-transplant Optimization Program (R-POP)

Version 1.18: October 25, 2022

social support are less often evaluated. This investigation will assess these five domains and implement interventions to improve them.

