3.5 Subject Recruitment, Selection, and Consent

Potential patient subjects will be recruited from the Duke Adult Bone Marrow Transplant (ABMT) Program. Under the current standard of care practice, ABMT physicians evaluate all new patients. If the patient's ABMT physician deems the patient to be an allogeneic transplant candidate and suitable for Research POP (R-POP), and the patient expresses interest in participating, they will be referred to research staff, who will review inclusion/exclusion criteria and tell the patient more about the study. Both the ABMT physician, who will be a sub-investigator, and the research staff will make clear that participation in this trial is voluntary, and patients may decline to hear more or to participate without penalty; these patients will receive standard of care.

Those interested in learning more will meet with study staff who will explain details, answer questions, and confirm inclusion/exclusion criteria. Only subjects who voluntarily provide full informed consent will be included in the study.

Subjects who are screened but do not want to participate (do not give informed consent) will not be recorded and will receive standard care. They will be asked to complete a decline survey (Appendix D) in order to inform the investigators of why participation was declined and improve study design for future interventions.

Caregiver subjects will be identified by their patient as the patient's primary caregiver. They will be approached by study staff who will explain details, answer questions, and confirm inclusion/exclusion criteria. Only those who voluntarily provide full informed consent will proceed to study enrollment. Patients may decide to enroll without their caregivers deciding to enroll; in these cases, patients will participate in the study and caregivers will not participate in any research-related events. Caregivers may not enroll if their patient does not enroll.

This is a single arm feasibility study; all subjects will be assigned to the intervention group. We anticipate 35 patients will be consented and 30 patients to pass CPET/cardiology clearance to receive interval training. Up to 35 caregivers may consent and 30 caregivers participate, though this number may be lower depending on caregiver availability and consent.

A Research Program Targeting Pre-, Peri-, and Post-transplant Optimization Program (R-POP)

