4.8 Safety endpoints

Treatment-related mortality (TRM) and grade 3-4 adverse events as defined by the National Cancer Institute Common Terminology Criteria for Adverse Events (NCI-CTCAE) ¹³⁵ will be monitored that are related to study interventions (e.g. exercising).

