5.0 ANTICIPATED TOXICITIES

We do not anticipate any major toxicities occurring with participation in our investigation. The study interventions are evidenced-based and aimed at improving any health concerns the participants may have. To ensure the utmost safety of our participants going through exercise training (**as described above in section 4.1**) study staff will ensure that all patients who take beta-blockers will have taken their medication prior to training to avoid any blood pressure-related events.

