6.0 STATISTICAL CONSIDERATIONS

General Considerations: All analyses will be summarized using appropriate effect estimates, confidence intervals, and p-values. All secondary and additional analyses will be evaluated at the standard 0.05 significance level. Descriptive statistics, including graphical displays, will be used to summarize all study variables. For continuous variables, means, standard deviations, percentiles, ranges, box plots and histograms will be generated. For categorical variables, frequencies and proportions will be generated. For time to event variables, event rates and survival curves will be generated. Statistical analyses will be performed using SAS for Windows (Version 9.3 or above: SAS Institute, Cary, NC) and the R statistical computing platform (R Core Team 2013; <http://www.R-project.org/>).

Categorical outcomes will be analyzed using chi-square techniques and logistic regression modeling. Length of stay outcomes will be analyzed using generalized linear models with appropriate link functions. Continuous, longitudinal outcomes such as the FACT-BMT and EQ-5D-5L will be analyzed using linear mixed regression modeling. Other continuous results (such as PG-SGA and numbers of days exercised and amount of exercise per day) will be analyzed using standard t-test approaches and correlated with outcomes. We will analyze TRM and CTCAE using Kaplan-Meier methods, log-rank tests, and Cox proportional hazard regression modeling.

6.1 Analysis of the Microbiota:

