As noted in the exercise intervention section, in order to participate in the exercise intervention, subjects must first meet all inclusion and exclusion criteria and consent to participate, after which they will undergo cardiopulmonary exercise testing (CPET). CPET will be reviewed by a physician and subjects will not be able to participate in the intervention unless cleared by a physician. Therefore, not every patient who consents will participate in the intervention. Because our goal is to test the intervention in 30 patients, and assuming a 10% drop out rate (subjects who consent to participate but do not pass CPET testing), we will consent 35 subjects with the intent that 30 will participate in the intervention.

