Risks to subjects are reasonable in that risks are low (e.g. related to exercise or psychological distress associated with questionnaire) and the goal of this study is to address these and other risks that may be raised. In fact, it is potentially beneficial to identify and address these risks prior to transplant than during the stress of transplant when they may emerge.

Importance of the Knowledge to be Gained

Importance of the knowledge to be gained

The success of this feasibility study would inform the development of a randomized phase 2 trial of pre-transplant interventions to improve transplant outcomes. This could establish a new standard of care for the treatment of transplant patients.

Why the risks to subjects are reasonable in relation to the importance of the knowledge that reasonably may be expected to result

Treatment-related mortality with allogeneic transplant ranges from 10-30%, with more frail individuals (i.e. functional impairment) at higher risk of adverse events. This study is low risk and has the potential to lead to new interventions to reduce treatment related mortality, which would have a significant impact on health.

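### Section 6.0 plans Kaplan-Meier, log-rank and Cox for TRM and adverse events in a single arm of about 30 treated patients: no contrast is defined, and the intervention-related safety endpoint may have no events to analyse

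*Combined protocol and SAP*

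**What the plan says.** Section 6.0 sets the method: "We will analyze TRM and CTCAE using Kaplan-Meier methods, log-rank tests, and Cox proportional hazard regression modeling". It names no groups, covariates, time origin, horizon or fallback for sparse events. It adds that "All secondary and additional analyses will be evaluated at the standard 0.05 significance level".

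On design and size, section 3.5 states "This is a single arm feasibility study; all subjects will be assigned to the intervention group", and section 6.2 states "we will consent 35 subjects with the intent that 30 will participate in the intervention".

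On expected events, section 4.8 lists TRM and grade 3-4 adverse events that "will be monitored that are related to study interventions (e.g. exercising". No rate is given for them; section 5.0 says "We do not anticipate any major toxicities occurring with participation in our investigation". For TRM, section 2.0 says "Allogeneic HCT is associated with treatment related mortality (TRM) ranging from 20-30" per cent and section 7.0 says "Treatment-related mortality with allogeneic transplant ranges from 10-30" per cent, neither with a time horizon.

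The adverse-event definition varies. Section 4.8 has grade 3-4 events related to the intervention. The opening of section 7.0 has grade 1-4, also related. Section 7.1 requires every adverse event to be recorded, whatever its cause.

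**The concern.** Log-rank compares groups and Cox estimates the effect of a covariate. With one arm and neither specified, it is unclear what would be tested at the 0.05 level. Sections 4.7.6, 4.7.7 and 6.1 do mention home and standard or hospital care, but only for the microbiota, and section 6.0 does not carry that grouping over to TRM or adverse events.

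The methods also need events. If no trained patient has a related grade 3-4 event, the planned display is a flat curve with a zero standard error. Section 6.2 calls this a safety and feasibility study, and section 7.0 says its success would inform a randomised phase 2 trial. A flat curve without an interval could be read as evidence of safety when 30 patients cannot exclude a rate near 10%.

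**Working it through.** **Denominator.** Section 6.2 wants 30 treated and assumes 10% drop-out: 30/0.90 = 33.3, so 34. The stated 35 is close and slightly generous. Patients not cleared after exercise testing leave the study (section 3.2), so n = 30 is used.

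**Intervention-related grade 3-4 events.** The plan gives no rate p, so 1%, 2% and 5% are assumed.

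- P(0 events) = (1 - p)^30: 0.99^30 = 74%, 0.98^30 = 55%, 0.95^30 = 21%.
- P(at most 1 event) = (1 - p)^30 + 30p(1 - p)^29: 96%, 88%, 55%.
- With zero events, every term of the Greenwood variance is zero, so the curve has no usable interval. Log-rank and Cox have nothing to work on.
- With one event, a Cox estimate for any binary factor is non-finite, because one level has no events. With two events and a 15/15 split, both fall in the same level with probability 2 × C(15,2)/C(30,2) = 210/435 = 48%.
- Over all event counts, for a 15/15 factor with no true effect, P(non-finite) = 2q^15 - q^30 with q = 1 - p: 98%, 93% and 71% at 1%, 2% and 5%.

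**Exact (Clopper-Pearson) 95% intervals, n = 30.** The upper limit for 0/30 is 1 - 0.025^(1/30) = 11.6%. For 1/30 the interval is 0.1-17.2%, and for 2/30 it is 0.8-22.1%. All are finite, including at zero.

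**TRM.** Expected events are 30 × 0.10, 0.20 and 0.30 = 3, 6 and 9. This assumes that all 30 are transplanted and that the quoted TRM is reached within follow-up. The fourth column uses the formula above. The fifth assigns each patient to a level at random with probability one half: 2(1 - p/2)^30 - (1 - p)^30. The interval factor is what a finite hazard ratio is multiplied and divided by, approximately exp(1.96 × 2/√d) for d events. Power is for a log-rank test of hazard ratio 2, balanced factor, two-sided 5%.

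| TRM | Expected events | Exact 95% CI at that count | Non-finite Cox, fixed 15/15 | Non-finite Cox, random 50:50 | Interval factor | Power, HR 2 |
|---|---|---|---|---|---|---|
| 10% | 3 | 2.1-26.5% | 37% | 39% | 9.6 | 9% |
| 20% | 6 | 7.7-38.6% | 7% | 8% | 5.0 | 13% |
| 30% | 9 | 14.7-49.4% | 0.9% | 1.5% | 3.7 | 18% |

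A simulation of 3,000 Cox fits per setting gave non-finite estimates in 36%, 7% and 0.8% for the fixed split, and median interval factors of 9.6, 5.5 and 3.9. For an uneven 6/24 factor, the non-finite share rises to 57%, 27% and 12%. Power of 80% for hazard ratio 2 would need 66 events.

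**The case against.** The strongest reply is that section 6.0 already promises effect estimates and confidence intervals for all analyses, proportions for categorical variables and event rates for time-to-event variables, so a count with an interval is within the plan. Safety decisions rest on continuous review by the principal investigator and annual committee review (sections 7.4.1 and 7.4.2), not on Cox. The primary hypothesis is session completion, and no decision rule depends on these models.

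Most of that stands, and it limits the weight of the point. It does not settle it. The general promise names no interval method that works at zero events, and the usual normal-approximation interval for 0/30 also has zero width.

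Three stronger readings are tempting but are not supported:

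- A reader might infer from section 5.0 that the plan itself forecasts almost no training-related events. It gives no number. At a true rate of 5%, zero events has only a 21% chance, and under the wider definitions in sections 7.0 and 7.1 the counts would be higher.
- A reader might infer that Cox will usually fail for TRM. For one balanced factor this is common only near 10%. At the 20-30% in section 2.0 it happens in about 7-8% and 1-2% of trials.
- A reader might infer from objective 1.2.1 an overfitted model with eight covariates. That objective lists parameters on which to gather information; the plan commits to no such model.

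**Conclusion.** The point holds in this form. Log-rank and Cox have no defined contrast for TRM or adverse events, whatever the event count. For intervention-related grade 3-4 events, the planned methods give no usable result in 74%, 55% or 21% of trials at assumed rates of 1%, 2% or 5%, whereas an exact interval always gives one. This half depends on those assumed rates and on reading section 6.0's unqualified CTCAE as the section 4.8 endpoint.

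For TRM, the 3-9 expected events leave very wide intervals and power of 9-18% for a doubling of hazard; non-finite estimates are a frequent problem only at the low end of the range or for uneven factors. The count would be lower if some patients are not transplanted, if the quoted TRM is reached only after follow-up ends, or if section 4.8 limits TRM to deaths related to the intervention. The primary feasibility analysis is unaffected.

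**What to change.** In section 6.0:

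1. Report intervention-related grade 3-4 events as the number and proportion of trained patients with at least one event, with an exact (Clopper-Pearson) 95% interval. State in advance that 0/30 excludes only rates above about 12%. Drop log-rank and Cox for this endpoint.
2. Report TRM descriptively with an interval, for example 6/30: 7.7-38.6%. Treat any log-rank or Cox analysis as exploratory, and run it only for a single prespecified factor.
3. Reconcile sections 4.8, 7.0 and 7.1, and say which adverse-event definition is analysed.

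Items 1 and 2 are changes of wording and need no extra patients or data. Item 3 needs a decision from the investigators, as does the choice of a factor if any model is kept. The small downside is that model-based results are given up and the safety statement carries a visibly wide upper limit.

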To analyze the gut microbiome, DNA will be extracted from fecal samples¹³⁰ and gut flora bacterial density will be quantified using real-time quantitative polymerase chain reaction (qPCR) as described.¹³¹ We will amplify 16S ribosomal RNA (rRNA) using Illumina HiSeq platform and analyze the data using the Qiime script package with parallel processing.¹³² Sequences will be de-noised and clustered at 97% identity using USEARCH and aligned to the 16S rRNA gene, using the align.seqs.py wrapper with the PyNAST algorithm and Greengenes reference alignment. Based on these results, we will calculate diversity (Shannon Diversity, primary endpoint, and Chao1) and construct phylogenetic trees using computational analysis software. Pairwise comparisons will be made between pre- and post-HCT samples and in-home vs. standard care groups. We will also make longitudinal evaluations within individual patients.

4.7.7 Skin swab and Microbiota Assessment:

A Research Program Targeting Pre-, Peri-, and Post-transplant Optimization Program (R-POP)

Skin samples will be obtained prior to conditioning and at day 30, 60 and 100 post HCT among 15 patients undergoing standard and 15 patients undergoing home transplant protocol.

Skin microbiota assessment will include a sample of a 2×2-cm area of the target region collected by swabbing the skin to pick up bacteria located on the skin. Specimens may be obtained from the following sites: (1) Forearm, antecubital fossa, (2) Retroauricular region, (3) Buccal, (4) Back, (5) Abdomen, (6) If applicable, areas with active GVHD or rash. Samples will be snap frozen and stored for batch sequencing and microbiome analysis. Subjects will also be offered to consent to the Duke Data and Specimen Repository (IRB Pro00006268) for storage of excess or unused specimens; if no consent to store the samples is obtained, the excess samples will be destroyed.

Additionally, because co-habitation may affect the microbiota of the involved individuals, we will also collect stool and skin samples from caregivers to analyze in conjunction from stool and skin samples from patients as described above. Samples will be collected as per Table 2. Samples not used during this research will be stored in the Duke Data and Specimen Repository (IRB Pro00078566) unless the caregiver does not consent to the Repository. If no consent to store the samples is obtained, the excess samples will be destroyed.

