Shannon diversity index will be compared using unpaired two-sided Student's *t* tests with a more stringent cut-off of 0.0125 given multiple comparisons, by the Bonferroni correction for 4 time periods of independent comparisons. Comparisons of bacterial populations will be made by using the Adonis non-parametric method from within the Qiime package using Unifrac distance matrices from the populations being compared. P values will be calculated with $\alpha=0.05$. Metastats will be used for further statistical analyses of population structure, membership, and diversity with metadata such as time from transplant and dietary measurements such as caloric intake¹⁴⁵. Changes in specific bacterial families of interest will be compared using a two-sided Student's *t* test, with normality confirmed by D'Agostino and Pearson omnibus test with $p \leq 0.05$. All other comparisons will be done using two-sided Mann-Whitney tests. The R packages vegan¹⁴⁶, phyloseq¹⁴⁷, APE¹⁴⁸, randomForest¹⁴⁹, and arules¹⁵⁰ will be used for identification of associative patterns between taxa most associated with home care and hospital care recovery and other care and disease-related metadata. Comparisons will also be made between pairs of patients and caregivers to determine these effects.

6.2 Power and sample size calculations:

The primary hypothesis of interest for this safety and feasibility study is that at least 50% of enrolled patients will complete more than 50% of their high intensity interval training sessions. With a sample size of 35 patients, our study will be able to estimate a completion rate of 50% to within a 95% confidence interval of +/- 19%. For higher completion rates, such as 75%, we will be able to estimate to within a 95% confidence interval of +/- 17%¹⁵¹.

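### Section 6.1 gives Shannon diversity only an unadjusted unpaired t test, so a pre-transplant gap between home-care and standard-care patients would carry into the post-transplant comparison

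*Combined protocol and SAP*

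**What the plan says.** Section 6.1 gives one method for this measure: "Shannon diversity index will be compared using unpaired two-sided" Student's t tests, "with a more stringent cut-off of 0.0125 given multiple comparisons", set "by the Bonferroni correction for 4 time periods of independent comparisons". The sentence does not say which groups are compared or which four periods are meant, and it lists no covariate.

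The contrasts appear in section 4.7.6: "Pairwise comparisons will be made between pre- and post-HCT samples and in-home vs. standard care groups". That section also adds "We will also make longitudinal evaluations within individual patients", and makes Shannon diversity the lead measure of the microbiome work ("we will calculate diversity (Shannon Diversity, primary endpoint, and Chao1"). Section 6.1 refers to home and hospital care only later, when it describes the search for taxa patterns.

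The assessment table in section 4.0 schedules stool at the six main timepoints plus days 0, 7, 14, 21 and year 2. Two of the six main timepoints, new patient evaluation and sign-off, come before transplant. Section 3.5 describes a single-arm study. Section 6.0 assigns linear mixed models to continuous longitudinal outcomes, with FACT-BMT and EQ-5D-5L as its examples.

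**The concern.** An unpaired test of post-transplant level is a fair estimate of a care-setting effect only if the groups were alike before transplant. No document says how a patient comes to home or standard care, so this cannot be taken for granted. If home-care patients start with higher diversity, part of that head start reappears after transplant and is read as an effect of the setting. If they start lower, a real benefit can be masked. The value needed to correct for this is already scheduled, but the specified test does not use it.

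**Working it through.** **The plan's own figure.** Section 6.0 sets "All secondary and additional analyses will be evaluated at the standard 0.05 significance level". With four comparisons, 0.05 / 4 = 0.0125, as stated. The documents give no SD, effect size, power or correlation for Shannon diversity, so there is no power figure to reproduce.

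**Inputs.**
- Two-sided alpha 0.0125 (section 6.1).
- 15 per group: stated in section 4.7.7 for skin samples only; assumed here for stool.
- rho, the correlation between pre- and post-transplant Shannon: not given; range 0 to 0.7.
- Baseline gap of 0.5 or 1 SD, and care effect of 1 SD: assumed.

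**Bias of the unadjusted test.** Write the post-transplant value as rho × baseline + residual + care effect, with within-group SD 1. The expected group difference is then care effect + rho × gap. With no care effect, all of rho × gap is bias.

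**False-positive rate.** The standard error of the difference is √(2/15) = 0.365 SD, and the critical t on 28 df is 2.669. The noncentrality is rho × gap / 0.365. For a 0.5 SD gap at rho 0.5 it is 0.25 / 0.365 = 0.685, and the two-sided rejection rate is 3.3%.

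| rho | bias, 0.5 SD gap | unadjusted | bias, 1 SD gap | unadjusted | adjusted |
|---|---|---|---|---|---|
| 0 | 0 | 1.25% | 0 | 1.25% | 1.25% |
| 0.3 | 0.15 | 1.9% | 0.30 | 4.3% | 1.25% |
| 0.5 | 0.25 | 3.3% | 0.50 | 11.5% | 1.25% |
| 0.7 | 0.35 | 5.6% | 0.70 | 24.6% | 1.25% |

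The adjusted column is nominal by construction, because baseline Shannon is the only confounder in the model.

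**Power for a 1 SD care effect, balanced baselines.**
- Unadjusted: noncentrality 1 / 0.365 = 2.739, power 53.5%.
- Adjusted: residual variance is multiplied by 1 − rho², one df is lost (27 df, critical t 2.676), and the average penalty for chance imbalance is 1 + 1/26. The variance factor is (2/15)(27/26) = 0.1385. At rho 0.5 the noncentrality is 1 / √(0.75 × 0.1385) = 3.10, power 66.5%.
- Across rho 0, 0.2, 0.3, 0.5 and 0.7, adjusted power is 51.4%, 53.5%, 56.2%, 66.5% and 85.2%.

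**Power with a 1 SD baseline gap.** Estimating the slope across unequal groups costs precision. The variance factor becomes 2/15 + (1 + 2/15)/26 = 0.1769. Adjusted power is then about 44%, 54% and 74% at rho 0.3, 0.5 and 0.7. Simulation of the same model gives 45%, 55% and 74%. The unadjusted test rejects more often here only because the gap adds to the effect, so its rejection rate is not usable power.

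**The four periods.** Section 4.7.7 says "Skin samples will be obtained prior to conditioning and at day 30, 60 and 100 post HCT": four times, the first before transplant. Stool is scheduled at 6 + 5 = 11 times. The count of four therefore matches the skin schedule and not the stool schedule, and section 6.1 does not say which is meant.

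**The case against.** Several stronger readings are tempting, and the documents do not support them.

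- **That section 6.1 itself tests home against standard care.** The Shannon sentence names no groups. The link is inferred from section 4.7.6, which also lists pre- versus post-transplant comparisons. Applied to those, an unpaired test would raise a different problem, because the samples are paired.
- **That the plan ignores each patient's pre-transplant value.** Section 4.7.6 plans pre/post comparisons and within-patient evaluations, and the mixed-model wording in section 6.0 is open-ended. What stands is narrower: section 6.1 gives no method for those analyses, and they do not adjust the group test.
- **That the groups are known to be non-randomised.** A single-arm design shows only that this study does not allocate care setting. How patients reach home care is not described.
- **That power is certainly lost.** This depends on rho. At 0.2 or below nothing is gained, and at 0 about 2 points are lost. Where the baseline gap is large, adjusted power falls below the balanced-case figures.
- **That one test is spent on baseline.** This holds only if the four periods are the skin-sampling times.

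It can also be said that no objective in section 1 compares care settings and that the groups are barely defined. This is fair, and it is why naming the contrast is part of the fix. None of it supports leaving a two-group test unadjusted when the baseline value is scheduled.

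**Conclusion.** The point holds in a limited form. The only test specified for Shannon diversity is unpaired and unadjusted, its groups and periods are not named, and under the natural two-group reading a baseline gap passes into the result as rho × gap. For a moderate gap of 0.5 SD the inflation is modest: from 1.25% to between 1.9% and 5.6% per test over rho 0.3 to 0.7. For a 1 SD gap it reaches 4.3% to 24.6%. At rho 0 there is no bias. The main gain from adjustment is less bias; extra power is a bonus that depends on rho. These sizes rest on assumed group sizes of 15 for stool, assumed gaps and an assumed range for rho.

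A reader might infer from the label in section 4.7.6 that the trial's primary endpoint is affected. It is not: Shannon diversity leads only the microbiome analysis, and the primary hypothesis in section 6.2 concerns completion of training sessions. The change should be made, but the study's main conclusion does not depend on it.

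**What to change.** In section 6.1:

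1. Name the contrast tested on Shannon diversity and list the post-transplant stool times that form the tested periods. Do not count a pre-transplant sample among them, and reset the Bonferroni divisor if the number changes.
2. For home versus standard care, replace the t test with ANCOVA, or with the linear mixed model of section 6.0, of post-transplant Shannon diversity on group. Use the sign-off Shannon value as covariate, or the new-patient-evaluation value where sign-off is missing.
3. State the method for the pre/post and within-patient analyses planned in section 4.7.6.
4. Label the care-setting contrast as non-randomised unless its allocation is documented.

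The cost is SAP wording. No new samples are needed. Adjustment uses one degree of freedom and loses about 2 points of power if rho is near 0. It removes only the measured gap in Shannon diversity; other differences between home-care and standard-care patients remain, and the report should say so.

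### Section 6.1 states the normality condition for the bacterial-family t-test backwards: D'Agostino-Pearson p ≤ 0.05 rejects normality and cannot confirm it

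*Combined protocol and SAP*

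**What the plan says.** Section 6.1 (Analysis of the Microbiota) names the test for bacterial families: "Changes in specific bacterial families of interest will be compared using a two-sided Student's *t* test". The condition that the section attaches to this choice of test is "with normality confirmed by D'Agostino and Pearson omnibus test with $p \leq 0.05". The sentence that follows it reads "All other comparisons will be done using two-sided Mann-Whitney tests". Nothing in the section says that a family failing the normality check moves to Mann-Whitney; the reader has to infer it from the order of the two sentences.

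Section 4.7.6 (Stool Collection and Microbiome Analysis) describes the contrasts: "Pairwise comparisons will be made between pre- and post-HCT samples and in-home vs. standard care groups". Section 4.7.7 (Skin swab and Microbiota Assessment) gives the only group sizes, "among 15 patients undergoing standard and 15 patients undergoing home transplant protocol". No split is given for stool. Section 6.0 sets 0.05 as the level for secondary and additional analyses. No other section restates or corrects the normality criterion.

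**The concern.** The D'Agostino-Pearson omnibus test takes normality as its null hypothesis, so a small p-value speaks against normality. The sentence makes a small p-value the condition for calling normality confirmed. The word for confirmation shows the intent, but the threshold says the opposite.

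This is an operative rule for choosing a test. An analyst who follows it literally uses the t-test on skewed families and turns normal ones away from it. An analyst who follows the intent departs from the written plan. What is at stake is some power, and a clear record of how each test was chosen, in the bacterial-family comparisons.

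**Working it through.** **A figure in the same section that can be reproduced.** The Shannon cut-off is Bonferroni over four periods: 0.05 / 4 = 0.0125, as stated. It does not depend on the normality rule.

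**Direction of the test.** The statistic is K² = Z(skewness)² + Z(kurtosis)², referred to chi-square on 2 degrees of freedom, so p = exp(−K²/2). Then p ≤ 0.05 means K² ≥ −2 ln 0.05 = 5.99, that is, large departures in skewness or kurtosis. The written condition selects non-normal samples.

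**How often a single sample meets the written condition.** Simulated with 10,000 samples per cell. The shapes are assumptions, because the documents give none.

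| Data | n = 15 | n = 30 |
|---|---|---|
| Normal | 5.5% | 5.7% |
| Log-normal, log-SD 1 | 66.9% | 93.6% |
| Exponential | 47.7% | 78.3% |

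These are rates for one sample. If both groups of a two-group comparison must meet the condition, the log-normal rate at n = 15 is about 0.67 × 0.67 = 0.45; simulation gives 45% to 46%. For normal data it is below 1%.

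**Power under the two directions.**
- Inputs from the documents: 15 per group (Section 4.7.7, skin) and two-sided 0.05 (Section 6.0).
- Assumptions: log-normal abundances; a true shift of two-thirds of the log-SD; Mann-Whitney for families that fail the check.
- Literal rule: t-test if both groups have p ≤ 0.05, otherwise Mann-Whitney.
- Corrected rule: t-test if both groups have p > 0.05, otherwise Mann-Whitney.
- 40,000 runs per cell. A separate run of 20,000 agrees to within about 0.6 points.

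| Comparison, 15 per group | log-SD 0.5 | log-SD 1 | log-SD 1.5 |
|---|---|---|---|
| Single time, literal / corrected | 37.4% / 41.9% | 30.0% / 39.8% | 21.5% / 39.4% |
| Loss (points) | 4.5 | 9.8 | 17.9 |
| Change score, pre/post correlation 0 | 23.2% / 24.9% | 20.9% / 23.5% | 16.4% / 23.1% |
| Loss (points) | 1.7 | 2.6 | 6.7 |
| Change score, log-scale correlation 0.5 | 40.2% / 42.5% | 34.3% / 39.6% | 24.5% / 37.9% |
| Loss (points) | 2.3 | 5.3 | 13.4 |

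For truly normal data with the same standardised shift, the figures are 38.8% and 42.3%, a loss of 3.5 points.

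**Type I error.** When the two groups have the same shape under the null, the literal rule rejects in about 2.5% to 4.5% of runs, so it is not anti-conservative in that case.

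**The case against.** The best defence is that nobody would be misled. The sentence shows its intent, 0.05 was probably meant as the level of the normality test, and harm needs an analyst to run a t-test because normality was rejected. This is fair and is why the severity is low. It does not make the sentence right: it ties the small p-value to confirmation, and no other section supplies the correct direction.

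A second objection is that the literal rule modelled above is partly constructed, since the move to Mann-Whitney is inferred. That stands. So does the point that the distribution, shift and correlation are all assumed, so the losses do not establish an effect size for this trial.

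Three stronger readings are tempting, and the documents do not support them.

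- **A much larger loss for within-patient changes.** With 21 to 24 evaluable patients, correlation 0.5 and log-SD 1.5, a loss of about 31 to 33 points can be produced, but only by assuming a signed-rank fallback, which the plan does not name. With the Mann-Whitney test that it does name, the loss in that setting is about 19 points. The patient numbers are also soft. They take 30 treated patients less the 20% to 30% treatment-related mortality in Section 2.0 (30 × 0.7 = 21; 30 × 0.8 = 24). Section 7.0 gives 10% to 30%, which allows 30 × 0.9 = 27, and stool is scheduled on days 0, 7, 14 and 21, so patients who die later could still contribute early post-transplant samples.
- **Two-thirds or more of comparisons sent to the wrong test.** The 67% is a rate for single samples. For a two-group comparison under the same assumptions it is about 46%.
- **Mann-Whitney misapplied to paired data.** Section 4.7.6 does plan pre- versus post-transplant comparisons, but Section 6.1 does not say that family changes are tested within patients by Mann-Whitney. The changes may be scores compared between groups, where an unpaired test is suitable. This is an ambiguity to close, not a demonstrated error.

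**Conclusion.** The normality condition in Section 6.1 is reversed, and this follows from the test's null hypothesis without any assumption. The size of the consequence does rest on assumptions: about 4 to 18 points of power for single-time comparisons and about 2 to 13 points for between-group change scores, given 15 per group, log-normal abundances with log-SD 0.5 to 1.5, a shift of two-thirds of the log-SD, and an inferred Mann-Whitney fallback.

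A reader might infer that the error inflates false positives or weakens the main result. Neither follows. The literal rule does not exceed 5% when the groups have the same shape under the null. The primary hypothesis on session completion and the Shannon comparison at 0.0125 do not use the rule. The matter is confined to a secondary microbiota analysis: wrong as written, low severity.

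**What to change.** In Section 6.1, change the condition to p > 0.05 and describe it as normality not rejected. Add that families failing it are compared by Mann-Whitney for unpaired contrasts and that, if any family contrast is within-patient before versus after transplant, Wilcoxon signed-rank is used. Say which contrasts are of which kind.

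The cost is one or two sentences and no new data. Two limits should be accepted openly:

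- A p-value above 0.05 does not prove normality. At n = 15 about a third of log-normal samples with log-SD 1 still pass (100% − 66.9% = 33.1%). Naming a rank or permutation test in advance would avoid the pre-test altogether.
- Rank tests do not test means. With equal means but unequal spreads at 15 per group, the corrected rule rejects in 23% to 60% of runs, against 13% to 48% for the literal rule. Rank-test results should therefore be reported as such, not as differences in means.
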